3.6. Safety results

Among 36 patients evaluable for first cycle Dose Limiting Toxicities, 3 DLTs were reported: grade 3 anemia, at 4 mg/m²/week; grade 4 hypertensive crisis, at 20 mg/m²/week; grade 3 fatigue, at 135 mg/m²/week [16].

The most frequent treatment emergent adverse events (TEAEs) reported in at least 15% of patients were fatigue (57.9%), anaemia (44.7%), nausea (31.6%), decreased appetite (28.9%), constipation, pain, vomiting (23.7% each), cough (21.1%), diarrhea (18.4%) and dyspnea (15.8%) [16].

The most frequent TEAEs related to NMS-01940153E reported in at least 10% of patients were anaemia (36.8%), fatigue (28.9%), nausea (21.1%), decreased appetite (15.8%), neutropenia (13.2%) and diarrhea (10.5%) [16].

Among the 4 patients treated at 67.5 mg/m²/week, the TEAE related to NMS-01940153E reported were nausea (2 patients G1), anemia (1 patient G2), decreased appetite (1 patient G1), fatigue (1 patient G1) and platelet count decreased (1 patient G3) [16].

Among the 7 patients treated at 135 mg/m²/week, the TEAE related to NMS-01940153E reported were anemia (1 patient G3, 3 patients G2), neutropenia (4 patients G3), decreased appetite (2 patients G2, 1 patient G1), diarrhoea (2 patients G2, 1 patient G1), fatigue (1 patient G3, 1 patient G2), nausea (1 patient G2, 1 patient G1), haemolysis (1 patient G1), keratitis (1 patient G3), mucosal inflammation (1 patient G3) and pain (1 patient G2) [16].

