5.2.1. Definition of DLTs

For this protocol, a DLT will be defined as any of the following events for which the relationship to NMS-01940153E cannot be definitely excluded. Toxicities are to be graded according to the NCI CTCAE version 5.0 [21].

Table 1. DLT criteria	
Hematological Toxicity	
Neutropenia	Grade 4 lasting >7 days or Grade 4 of any duration associated with Grade ≥ 2 infection
Febrile neutropenia	ANC <1000/mm ³ and a single temperature of >38.3 degrees C or a sustained temperature of ≥ 38 degrees C for more than one hour.
Thrombocytopenia	Grade 3 associated with any grade bleeding or Grade 4
Anaemia	Grade ≥ 4
Non-Hematological Toxicity	
Nausea, vomiting or diarrhea	Grade ≥ 3 despite optimal treatment
Signs of potential severe drug-induced liver injury as assessed according to Hy's law	Alanine aminotransferase (ALT) or aspartate aminotransferase (AST) >3 ULN and total bilirubin >2 ULN in the absence of cholestasis (alkaline phosphatase [ALP] <2 ULN) and no other reason can be identified.
Any other non-hematological toxicities;	Grade ≥ 3 toxicities unless clear alternate etiology is documented by the investigator and except: - asymptomatic Grade 3 electrolyte changes that can be successfully supplemented (e.g., hypokalemia) and resolve/recover to baseline within 72 hours - Grade 3 fatigue that improves to \leq Grade 2 in no more than 5 days - alopecia
Other significant toxicity	
Failure to complete the first cycle of treatment with at least 66% of the planned total dose due to toxicity possibly related to the study medication	-
Failure to start Cycle 2 for more than 1 week (day 36 or later) due to persistent Grade ≥ 2 toxicities possibly related to the study medication, excluding fatigue	-
Any toxicity that is possibly related to the study medication and requires the withdrawal of the patient from the study during the DLT observation period	-
Any on-study death not clearly due to the underlying disease or extraneous causes	-

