5.3. Phase II

The Phase I part of the trial ended on May 30th, 2022 with the declaration of an RP2D of 100 mg/m²/week, and the study has already received a unanimous recommendation from an independent Data Safety Monitoring Board (DSMB) to continue the trial, moving to Phase II study.

The RP2D of 100 mg/m²/week, 3 of 4 weekly schedule, is justified based on safety, efficacy and pharmacokinetic considerations. The trend of dose-related neutropenia as the major safety feature points to the 100 mg/m²/week level as more tractable relative to 135 mg/m² (refer to full safety summaries in the IB). In terms of anti-tumor activity, the fact that, out of 6 evaluable, one confirmed RECIST partial response (despite one missed dose during the first two cycles) plus one highly prolonged stable disease were observed at 100 mg/m² as well as, out of 4 evaluable, 2 patients with substantial AFP reduction were observed points to reasonable activity at this dose level. Furthermore, pharmacokinetics at the 100 mg/m² dose level are in a meaningful range relative a continuous mouse tumor stabilization model predicting 0.2 uM average concentration threshold relative to the 100 mg/m² mean Cmax in HCC patients which is 7 fold higher at 1.35 uM and with AUC just slightly below the mouse threshold, 32.5 uM*h versus 35. Refer to IB for full PK descriptions. RECIST response and AFP reductions were observed at the 135 mg/m²/w level and PK was slightly higher but overall the anti-tumor pattern at 135 was similar to 100 mg/m². Therefore, overall, the 100 mg/m² level is justifiable as the RP2D.

In the Phase II portion, patients will receive the RP2D defined in the Phase I portion of the study as starting dose.

As soon as signs of toxicity are observed requiring a dose de-escalation, the dose will be decreased as described in Section 9.2.3.1, Table 6). A maximum of two dose decreases will be allowed, otherwise patient will have to be withdrawn from the study.

Patients will be enrolled in continuous, and continuously evaluated for endpoints, with a futility analysis and stopping criteria for unacceptable toxicity performed as described in Section 12. The enrollment will be stopped in the event of futility as described in Section 12, with no more than 20 subjects treated overall until non-futility can be declared, if appropriate. In any case, the Sponsor may stop or pause enrollments any time during the study based on safety, efficacy or strategic reasons.

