12.4. Interim Analysis Plan

In the Phase II part of the study an interim evaluation for futility will be undertaken as soon as the first 10 evaluable patients will be enrolled and the data for primary efficacy endpoint analysis will be available including observations through at least 3 months with at least 1 on-treatment tumor assessment by RECIST 1.1. If less than 1 responder i.e., patients who achieved CR or PR as best overall response, are observed, the study will be terminated for futility. This futility decision must be taken before 20 subjects total are enrolled otherwise enrollment will pause at 20 subjects until non-futility can be declared (if applicable). If at least 1 unconfirmed or confirmed responder is observed and there are no safety limitations, patients' enrollment will continue and proceed up to an overall enrollment of 38 evaluable patients or 40 total patients. For the safety monitoring, if two or more patients on study experience Grade 4 adverse events the study will be put on hold to evaluate whether to continue or if additional risk mitigation is warranted. The independent DSMB will review the interim results and provide a recommendation on the study progress.

Notification of the temporarily interruption of recruitment as well as restart of enrollment will be notified to the IECs.

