5.2. Planned Schedule of Interim Analyses

In the Phase II part of the study an interim evaluation for futility will be undertaken as soon as the first 10 evaluable patients will be enrolled and the data for primary efficacy endpoint analysis will be available including observations through at least 3 months with at least 1 on treatment tumor assessment by RECIST 1.1 [2]. If less than 1 responder i.e., patients who achieved CR or PR as best overall response, are observed, the study will be terminated for futility. This futility decision must be taken before 20 subjects total are enrolled otherwise enrollment will pause at 20 subjects until non-futility can be declared (if applicable). If at least 1 unconfirmed or confirmed responder is observed and there are no safety limitations, patients' enrollment will continue and proceed up to an overall enrollment of 38 evaluable patients or 40 total patients. For the safety monitoring, if two

or more patients on study experience Grade 4 adverse events the study will be put on hold to evaluate whether to continue or if additional risk mitigation is warranted. The independent DSMB will review the interim results and provide a recommendation on the study progress.

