9.8.2. Dose Limiting Toxicities

A DLT will be defined as any of the adverse events described in MPSA-153-001 Clinical Protocol Section 5.2.1 occurring in Cycle 1, during Phase I dose escalation, for which the relationship to NMS-01940153E cannot be definitely excluded. Toxicities are to be graded according to the NCI CTCAE version 5.0 [13]. In particular:

Hematological Toxicity

- Neutropenia Grade 4 lasting >7 days or Grade 4 of any duration associated with Grade ≥ 2 infection
- Febrile neutropenia ANC <1000/mm³ and a single temperature of >38.3 degrees C or a sustained temperature of ≥ 38 degrees C for more than one hour.
- Thrombocytopenia Grade 3 associated with any grade bleeding or Grade 4
- Anaemia Grade ≥ 4

Non-Hematological Toxicity

- Nausea, vomiting or diarrhea Grade ≥ 3 despite optimal treatment
- Signs of potential severe drug-induced liver injury as assessed according to Hy's law: Alanine aminotransferase (ALT) or aspartate aminotransferase (AST) >3 ULN and total bilirubin >2 ULN in the absence of cholestasis (alkaline phosphatase [ALP] <2 ULN) and no other reason can be identified.
- Any other non-hematological toxicities: Grade ≥ 3 toxicities unless clear alternate etiology is documented by the investigator and except:
 - asymptomatic Grade 3 electrolyte changes that can be successfully supplemented (e.g., hypokalemia) and resolve/recover to baseline within 72 hours
 - Grade 3 fatigue that improves to \leq Grade 2 in no more than 5 days
 - alopecia

Other significant toxicity

- Failure to complete the first cycle of treatment with at least 66% of the planned total dose due to toxicity possibly related to the study medication
- Failure to start Cycle 2 for more than 1 week (day 36 or later) due to persistent Grade ≥ 2 toxicities possibly related to the study medication, excluding fatigue
- Any toxicity that is possibly related to the study medication and requires the withdrawal of the patient from the study during the DLT observation period

Statistical Analysis Plan

- Any on-study death not clearly due to underlying disease or extraneous causes

For the Phase I part only, first cycle DLT analysis will be performed on the dose-limiting toxicity evaluable set. For each dose level, patients who experienced a DLT during the first cycle of treatment and type of DLT experienced, will be reported in a data listing.

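### The Phase II safety hold counts Grade 4 events only, so read literally a patient with fatal toxicity and no recorded Grade 4 event does not count toward it

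*Protocol*

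**What the plan says.** Protocol 5.3 promises a futility analysis and "stopping criteria for unacceptable toxicity performed as described in Section 12". The only count-based toxicity rule in Section 12 is in 12.4: "if two or more patients on study experience Grade 4 adverse events the study will be put on hold", after which the need for further risk mitigation is evaluated. Protocol 1.4 states the same rule twice, once in the Phase II design text and once under Interim Analyses. SAP 5.2 repeats it without clarification: "or more patients on study experience Grade 4 adverse events the study will be put on hold".

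Two other Phase II provisions bear on safety. At the futility interim, enrollment goes on only if a responder "is observed and there are no safety limitations". Under 5.3, "the Sponsor may stop or pause enrollments any time during the study based on safety, efficacy or strategic reasons".

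For Phase I, the criteria for dose-limiting toxicity (DLT) in Table 1 of Protocol 5.2.1 include a death criterion on its own line: "Any on-study death not clearly due to the underlying disease or extraneous causes".

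**The concern.** In this trial Grade 4 and Grade 5 are different grades; Table 12 in Protocol 11.5.1.9 lists life-threatening and fatal events separately. A rule that counts Grade 4 without adding worse grades or death therefore leaves out fatal events if applied as written. The trigger would respond to two life-threatening events but could stay silent after two toxic deaths.

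What is at stake is participant protection during continuous enrollment of up to 40 patients. The estimand, the sample size and the response-rate analysis do not depend on this rule.

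**Working it through.** The plan gives no operating characteristics for the hold, so there is no stated figure to reproduce. The check has three parts.

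**1. Wording compared across the documents**

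| Place | What counts | Grade 5 or death covered? |
|---|---|---|
| Protocol 1.4 (twice), 12.4; SAP 5.2: Phase II hold | Grade 4, no inequality sign or range | No |
| Protocol Table 1 and SAP 9.8.2: anaemia as a DLT | "Anaemia Grade ≥ 4" | Yes |
| Protocol Table 1: other non-hematological DLTs | Grade 3 or higher, with listed exceptions | Yes |
| Protocol Table 1: on-study death as a DLT | Separate line, with an attribution qualifier | Yes |
| Protocol 12.3.6 and SAP 9.8.1: adverse event tables | Grades 3 to 5 | Yes |

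**2. Who is left out**

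The hold counts patients, and Protocol 11.5.1.9 requires changes of grade within an event to be recorded. A toxicity recorded at Grade 4 before death already counts, and so does any other recorded Grade 4 event in that patient, whatever its cause. Only the patient with fatal toxicity and no recorded Grade 4 event of any kind is missed (Grade-5-only below).

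| Patients observed | Literal count | Hold? |
|---|---|---|
| 2 with Grade 4 | 2 | Yes |
| 1 with Grade 4, 1 Grade-5-only | 1 | No |
| 2 Grade-5-only | 0 | No |

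**3. Illustrative size**

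The documents give no Grade 4 or toxic-death rate for patients with hepatocellular carcinoma. The nearest data are the first-in-human results in Protocol 3.6, at the two doses that bracket the Phase II dose of 100 mg/m²: 4 patients at 67.5 mg/m² and 7 at 135 mg/m². The worst drug-related grade listed at either dose is 3; at 135 mg/m², for example, "the TEAE related to NMS-01940153E reported were anemia (1 patient G3, 3 patients G2), neutropenia (4 patients G3"). That is 0 of 11 patients at Grade 4 or 5. The exact one-sided 95% upper limit is 1 − 0.05^(1/11) = 0.238. This does not estimate the Phase II rate: the tumors were mixed, only related events were listed, and the hold counts events of any cause. Protocol 3.6 also reports one Grade 4 hypertensive crisis at 20 mg/m².

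Let a be the proportion of patients with a recorded Grade 4 event and b the proportion who are Grade-5-only. The two groups do not overlap, patients are treated as independent, and all values are assumptions. With n patients and p the counted proportion,

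P(hold) = 1 − (1 − p)^n − n·p·(1 − p)^(n−1),

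where p = a under the literal rule and p = a + b if Grade 5 also counts. Example with n = 20, a = 0.02, b = 0.01: the literal rule gives 1 − 0.98^20 − 20·0.02·0.98^19 = 0.060, and the inclusive rule with p = 0.03 gives 0.120. The values of n are the enrollment pause (20) and the Phase II cap (40).

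| n | a | Literal | b = 1% | b = 2% | Rise (points) |
|---|---|---|---|---|---|
| 20 | 2% | 0.060 | 0.120 | 0.190 | 6 to 13 |
| 20 | 5% | 0.264 | 0.340 | 0.413 | 8 to 15 |
| 20 | 10% | 0.608 | 0.662 | 0.711 | 5 to 10 |
| 20 | 23.8% | 0.968 | 0.975 | 0.980 | about 1 |
| 40 | 2% | 0.190 | 0.338 | 0.479 | 15 to 29 |
| 40 | 5% | 0.601 | 0.701 | 0.780 | 10 to 18 |
| 40 | 10% | 0.920 | 0.944 | 0.961 | 2 to 4 |
| 40 | 23.8% | 1.000 | 1.000 | 1.000 | 0 |

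**The case against.** The best reply is that no one would apply the rule this way. Investigators, sponsor and DSMB would not see two toxic deaths and decide that no hold is due. The intent was very probably Grade 4 or worse, and the hold only starts an evaluation that other routes would also start. Every death in the reporting period is a serious adverse event (Protocol 11.5.1.1.2), due to the sponsor within 24 hours, with expedited reporting of suspected unexpected reactions (11.5.1.7). The DSMB reviews safety periodically (12.5), and the sponsor may pause at will. This lowers the practical risk and stands as mitigation. It does not close the gap, because these are reporting duties, periodic reviews or matters of discretion, and the no-safety-limitations condition applies once, at the interim. If the intended rule differs from the written one, the text should be corrected.

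A second reply is that Table 1 itself uses Grade 4 without an inequality sign for neutropenia and thrombocytopenia, so the wording contrast is weak. Usage is indeed mixed. But Table 1 covers death on its own line, and the Phase II hold has no such line.

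A third reply concerns size, and it is fair. No document supports b of 1% to 2%. The 29-point rise needs a = b = 2%, so that half of all counted patients die without a recorded Grade 4 event. Protocol 5.3 names dose-related neutropenia as the main safety feature, which fits poorly with very rare Grade 4 events. The table shows how the gap behaves; it does not predict it.

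**Conclusion.** The concern holds as a wording error in a participant-safety threshold, of low to moderate severity. All four statements of the rule share it, and nothing else in Phase II supplies a count-based trigger for deaths. That conclusion rests on the text alone and needs no assumed rate. Nothing in the documents suggests that leaving out Grade 5 was deliberate.

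The practical size cannot be fixed from the documents. Over the assumed rates, the loss in the probability of a hold ranges from nil, when Grade 4 events are common, to 29 points in the least supported scenario.

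**What to change.** In Protocol 1.4 (both places), Protocol 12.4 and SAP 5.2, define the trigger as two or more patients who each have either a Grade 4 adverse event or a Grade 5 adverse event that meets the attribution test of the Table 1 death criterion. The threshold of two patients stays as it is.

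The qualifier is advisable because deaths from progression are also reported as serious adverse events and should not by themselves halt the study. It has a price: Grade 4 events would count whatever their cause, while deaths would first need a judgement on attribution. Plain wording of Grade 4 or higher would also close the gap and avoid that step, but it could bring progression deaths into the count.

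The cost is one phrase in four places, plus a possible extra pause for review. No analysis or sample size changes.

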12.5. Data Monitoring Committee

An independent DSMB will provide study oversight through periodic safety evaluations and make recommendations on study progress in the transition from Phase I to Phase II and at the planned interim analysis for the futility of Phase II.

During the Phase I part, teleconferences will be held at the end of each cohort between the Investigators and the Sponsor to review all relevant safety and PK data and take decision on the dose escalation to be applied to the next cohort of patients. Once the MTD is identified, and the safety profile of NMS-01940153E has been reviewed by the Investigators, the Sponsor and the independent DSMB and is considered adequate based on the Phase I data available, the RP2D will be defined and the Phase II portion of the study will start.

Two clinical experts in the field of hepatology or onco-hepatology and a statistician, who are not involved in the study and have no conflict of interest with respect to study results, will compose the independent DSMB.

Tasks of the independent DSMB will be:

- To provide a recommendation on study progress in the transition from Phase I to Phase II and at the planned interim analysis for the futility of Phase II, based on risk-benefit evaluation;
- To periodically review adverse events, serious adverse events and all other safety and pharmacokinetic data collected during the study;
- To suggest other toxicities to be recorded/monitored in the group of patients who will be enrolled after the independent DSMB safety evaluation.

13. END OF THE TRIAL

For the purpose of this study, the end of the trial is defined as the date of the last visit of the last patient, including follow up.

14. QUALITY CONTROL AND QUALITY ASSURANCE

The Sponsor assumes accountability for actions delegated to other individuals (e.g., Contract Research Organizations).

Study monitors will perform ongoing source data verification to confirm that data entered into the eCRF by authorized site personnel are accurate, complete, and verifiable from source documents; that the safety and rights of participants are being protected; and that the study is being conducted in accordance with the currently approved protocol and any other study agreements, ICH GCP, and all applicable regulatory requirements.

The Investigator must permit study-related monitoring, audits performed by the Sponsor or designee, IRB/IEC review, and regulatory agency inspections and provide direct access to source data documents.

It is important that the Investigator and his/her relevant personnel are available during the monitoring visits and possible audits or inspections and that sufficient time is devoted to the process.

The Sponsor or designee is responsible for the data management of the study including quality checking of the data. That means that following data entry or electronic receipt of data, data validation will take place and Forms/Reports for data clarifications will be addressed to the Investigator. Data management activities will address the coding and review of terms by scientific and clinically qualified staff.

15. DATA HANDLING AND RECORD KEEPING

15.1. Electronic Case Report Forms (eCRFs)

An eCRF must be filled in by the Investigator or authorized delegate for each enrolled and treated patient. Refer to Study Manual data entry instructions about data required for patients classified as screening failure or enrolled but untreated.

It is the Investigator's or authorized delegate's responsibility to ensure completion and to review and authorize release of the eCRF for each enrolled Clinical Trial Patient. The signature on the eCRF serves to attest that the information contained in the eCRF is true, accurate and reliable. At all times, the Investigator has full responsibility for the accuracy, legibility, completeness, and timeliness of all data (e.g., clinical data, laboratory results) reported in the eCRF and in the related data clarification tools (e.g., Data Clarification, Discrepancy Notes, Queries).

Source documents provide evidence for the existence of the participant and substantiate the integrity of the data collected. Source documents are filed at the Investigational Site. Source documents would include, but are not limited to, hospital/clinic records, physicians' and nurses' notes, appointment books, original laboratory result reports, ECG, x-rays, signed informed consent forms (ICF).

15.2. Record Retention

Any study records and documents, including signed ICFs, pertaining to the conduct of the study, must be retained by the Investigator for the period of time specified in the Clinical Trial Agreement, unless local regulations or institutional policies require a longer retention period.

No records may be destroyed during the retention period without the written approval of the Sponsor. No records may be transferred to another location or party without written notification to the Sponsor.

16. ETHICS

16.1. Institutional Review Board (IRB)/Independent Ethics Committee (IEC)

Clinical Study Protocol, Protocol Amendments, Informed Consent Forms, Investigator Brochure and other relevant documents (e.g., advertisements) must be submitted to IRB(s)/IEC(s) by the Investigator(s) and/or Sponsor/Delegate Party in accordance with local regulations reviewed and approved by the IRB(s)/IEC(s) before the study is initiated.

Any amendments to the protocol will require IRB/IEC approval before implementation of changes made to the study design, except for changes necessary to eliminate an immediate hazard to study participants. In that case, the Investigator must notify the IRB/IEC, the Sponsor or Delegated Party and Regulatory Authority, as applicable, as soon as possible after the implementation.

The Investigator will be responsible for the following:

- Providing written summaries of the status of the study to the IRB/IEC annually or more frequently in accordance with the requirements, policies, and procedures established by the IRB/IEC

- Notifying the IRB/IEC of SAEs or other significant safety findings as required by IRB/IEC procedures.

